New lesion response is classified as present or not ("Yes" or "No"). The response is "Yes" if there is at least one lesion that the investigator considers unequivocal new tumour.

CONFIDENTIAL Page 52 of 66

- Lesions that are equivocal (for example, due to small size) should not be considered new until they are confirmed by later scanning. Once confirmed, they can be retrospectively called new lesions at the time they were first seen.
- A lesion identified in an area not previously scanned is considered a new lesion.
- New lesions seen on nuclear medicine bone scans should be confirmed using anatomical imaging, whenever possible. If bone lesions are confirmed on later CT or MRI scan, progression should be assigned to the visit in which new lesion(s) were first seen on bone scan (in a manner similar to other equivocal new lesions). In the absence of structural confirmation, the pattern of lesions must clearly indicate metastasis, usually with at least two new lesions present.

Overall response is determined by combining the target, non-target, and new lesion responses.

| Table 9 | : | Response | Assessment |
|---------|---|----------|-------------------|
|---------|---|----------|-------------------|

| Target Lesions | Non-Target Lesions | New Lesions | Overall Visit Response |
|-----------------------|---------------------|-------------|---------------------------|
| CR | CR | No | CR |
| CR | Non-CR/Non-PD or NE | No | PR |
| PR | Non-CR/Non-PD or NE | No | PR |
| SD | Non-CR/Non-PD or NE | No | SD |
| PD | Any | Yes or No | PD |
| Any | PD | Yes or No | PD |
| Any | Any | Yes | PD |

After all visits have been evaluated, the sequence of overall visit responses is used to derive best overall response (BOR).

- BOR is defined as the best visit response recorded from the start of the treatment until disease progression/recurrence.
- ORR: It is defined as sum of CR and PR rates
- Clinical Benefit Rates: It is defined as sum of CR, PR and SD rates
- PFS is measured from the time of first dose of study drug to radiographic (or tumour marker as applicable) documentation of disease progression or death due to any cause.

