9 STATISTICAL METHOD AND CONSIDERATIONS

9.1 General Considerations

This section describes the statistical methods to be used to analyze efficacy and safety. These methods may be revised and updated due to reasons such as regulatory requirements or need for further clarifications. All statistical analyses will be performed using SAS 9.1 or higher. The final analysis plan will be documented in a formal statistical analysis plan (SAP) that must be finalized before database lock. The SAP will include details on how variables will be derived, how missing data will be handled, and how data will be presented as well as the details on statistical methods to be used for safety and efficacy analyses. The final clinical study report will discuss deviations from the SAP, if any.

CONFIDENTIAL Page 53 of 66

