9.4.3 Efficacy analyses

The efficacy endpoints will include:

- The percentage of patients without disease progression at the end of 6 months
- ORR: The percentages of CR+PR will be calculated and presented along with 95% confidence intervals of these percentages.
- CBR: The percentages of CR+PR+SD will be calculated and presented along with 95% confidence intervals of these percentages.
- PFS: It is defined as time from the first dose of study drug to documented disease progression or death due to any cause. This variable will be analyzed via Kaplan-Meier methodology.

CONFIDENTIAL Page 54 of 66

Additional efficacy parameters will be assessed depending on the emerging efficacy data. These analyses will be performed from time to time for presentation/publication purposes.

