5.2 Changes from the Analyses Planned in the Protocol

There were no changes in the analysis planned in the protocol of the study at the time of preparing this statistical analysis plan.

BASELINE, EFFICACY and Safety EVALUATIONS 6.

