6.4.2 Secondary Efficacy Variables

The best overall response is defined as the best visit response recorded from the start of the treatment until disease progression/recurrence. This data will be summarized using frequency and percentage for

CONFIDENTIAL Document Date: 12MAY2023. ST-AD-032 version 01

Complete Response (CR), Partial Response (PR), Stable Disease (SD), and Progressive Disease (PD) for each treatment group.

- Overall Response Rate (ORR): The percentages of CR+PR will be calculated and presented along with 95% confidence intervals of these percentages.
- Clinical Benefit Rate (CBR): The percentages of CR+PR+SD>=24 weeks will be calculated and presented along with 95% confidence intervals of these percentages.
- Progression Free Survival (PFS): It is defined as time from the first dose of study drug to documented disease progression or death due to any cause. This variable will be analyzed via Kaplan-Meier methodology.

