8.7.2 Analysis of Secondary Efficacy Variables

These secondary efficacy variables will be analysed and summarised to evaluate safety and tolerability of tenalisib.

• Overall Response Rate (ORR): It is defined as sum of CR and PR rates.

The percentages of CR+PR will be calculated and presented along with 95% confidence intervals of these percentages.

This data will be summarized using frequency, and percentage along with 95% confidence intervals of these percentages using exact method based on binomial distribution.

The corresponding listing will also be provided.

• Clinical Benefit Rate (CBR): It is defined as sum of CR, PR and SD at 24 weeks or longer.

The percentages of CR+PR+SD>=24 weeks will be calculated and presented along with 95% confidence intervals of these percentages.

This data will be summarized using frequency, and percentage along with 95% confidence intervals of these percentages using exact method based on binomial distribution.

The corresponding listing will also be provided.

Progression Free Survival (PFS): It is defined as time from the first dose of study drug to
documented disease progression or death due to any cause.
 PFS is measured from the time of first dose of study drug to radiographic (or tumour marker as
applicable) documentation of disease progression or death due to any cause. Patients who did not
progress or die will be censored on the last date the patient is known to be radiologically
progression free. The summary table for PFS rate at 6-Month and 1-year by metastasis type will
also be provided.

This variable will be analyzed via Kaplan-Meier methodology and displayed graphically for each treatment group and overall. The following reports will be generated:

- The Q1, median and Q3 PFS time will be provided. The 95% CI for the Q1, median, and Q3 PFS time will be presented for each treatment group and metastasis group using Brookmeyer-Crowley method.
- The number and % of patients with disease progressive events (further divided into progression or death) will be provided.
- The number and % of patients censored (further divided by reasons for censoring) will be provided.
- Kaplan-Meier curves will be produced.
- · A listing of PFS data will be provided.

Additional efficacy variables

Duration of Treatment: Duration of treatment is defined as the time from first dose to last dose of drug.

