- 1. Table 14.2.1.2 Summary of Patients without Disease Progression at the End of 6 Months by Type of Metastasis ITT Analysis Set <Column 1: same as table 14.2.1.1; Column 2: de novo metastasis; Column 3: recurrent metastasis; Column 4: Overall>
- 2. Table 14.2.1.3 Summary of Patients without Disease Progression at the End of 6 Months Per Protocol Analysis
- 3. Table 14.2.1.4 Summary of Patients with 6-Month and 1-Year Progression Free Survival ITT Analysis Set
 - <Column 1: First line "Number (%) of patients without Progressive disease/Death at 6 Month" Second line "Number (%) of patients without Progressive disease/Death at 1 year;

Add footnote-"At 1 year, patients with treatment duration ≥360 days are summarized."

- 4. Table 14.2.1.5 Summary of Patients with 6-Month and 1-Year Progression Free Survival by Type of Metastasis ITT Analysis Set
 - <Column 1: First line "Number (%) of patients without Progressive disease/Death at 6 Month"

 Second line "Number (%) of patients without Progressive disease/Death at 1 year;

Add footnote-"At 1 year, patients with treatment duration ≥360 days are summarized."

Column 2: de novo metastasis; Column 3: recurrent metastasis; Column 4: Overall>

5. Table 14.2.1.6 Summary of Patients with 6-Month and 1-Year Progression Free Survival – Per Protocol Analysis

^{*} The 95% CIs are reported using exact method based on binomial distribution.

Protocol RP6530-2101

Table 14.2.2.1

Summary of Objective Response Rate and Clinical Benefit Rate

ITT Analysis Set

	Tenalisib 800 mg BID	Tenalisib 1200 mg BID	Overall
	(N=xx)	(N=xx)	(N=xx)
Number (%) of patients			
95% CI*			
CR	xx (xx.x)	xx (xx.x)	xx (xx.x)
	(xx.x, xx.x)	(xx.x, xx.x)	(xx.x, xx.x)
PR	xx (xx.x)	xx (xx.x)	xx (xx.x)
	(xx.x, xx.x)	(xx.x, xx.x)	(xx.x, xx.x)
SD	xx (xx.x)	xx (xx.x)	xx (xx.x)
	(xx.x, xx.x)	(xx.x, xx.x)	(xx.x, xx.x)
SD>=24 weeks	xx (xx.x)	xx (xx.x)	xx (xx.x)
	(xx.x, xx.x)	(xx.x, xx.x)	(xx.x, xx.x)
PD	xx (xx.x)	xx (xx.x)	xx (xx.x)
	(xx.x, xx.x)	(xx.x, xx.x)	(xx.x, xx.x)
Not Evaluated	xx (xx.x)	xx (xx.x)	xx (xx.x)
	(xx.x, xx.x)	(xx.x, xx.x)	(xx.x, xx.x)
ORR (CR+PR)	xx (xx.x)	xx (xx.x)	xx (xx.x)
	(xx.x, xx.x)	(xx.x, xx.x)	(xx.x, xx.x)
CBR (CR+PR+SD>=24 weeks)	xx (xx.x)	xx (xx.x)	xx (xx.x)
,	(xx.x, xx.x)	(xx.x, xx.x)	(xx.x, xx.x)

The ITT analysis set includes all patients who received at least 1 dose of study medication. Percentages are based on the total number of patients (N) in each treatment group.

CONFIDENTIAL

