Page 42 of 106 ST-AD-032 version 01 Page xx of yy

* The 95% CIs are reported using exact method based on binomial distribution.

The BOR is defined as the best visit response recorded from the start of the treatment until disease progression/recurrence. The response rates (CR/ PR/ SD/SD>=24 weeks/PD) are estimated using (BOR) recorded in each patient. For the patients without any post-baseline efficacy assessment, BOR is considered as 'Not evaluated'.

For SD \geq 24 weeks, patients with treatment duration \geq 168 (\pm 7) days are summarized.

CR- Complete Response; PR- Partial Response; SD- Stable Disease; PD- Progressive Disease; ORR- Objective Response Rate; CBR- Clinical Benefit Rate. Reference Listing 16.2.x.x

Program: xx.sas Table Generation: ddmmmyyyy hh:mm:ss

Use same format for

Document Date: 12MAY2023.

1. Table 14.2.2.2 Summary of Objective Response Rate and Clinical Benefit Rate by type of metastasis – ITT Analysis Set <Column 1: same as table 14.2.2.1; Column 2: de novo metastasis; Column 3: recurrent metastasis; Column 4: Overall>

2. Table 14.2.2.3 Summary of Objective Response Rate and Clinical Benefit Rate – Per Protocol Analysis

CONFIDENTIAL Page 43 of 106 ST-AD-032 version 01

Protocol RP6530-2101 Table 14.2.3.1 Summary of Progression Free Survival ITT Analysis Set Page xx of yy

	Tenalisib 800 mg BID	Tenalisib 1200 mg BID	Overall
	(N=xx)	(N=xx)	(N=xx)
Number (%) of patients with Progressive Disease/Death	xx (xx.x)	xx (xx.x)	xx (xx.x)
Progressive Disease, n (%)	xx (xx.x)	xx (xx.x)	xx (xx.x)
Death, n (%)	xx (xx.x)	xx (xx.x)	xx (xx.x)
Number (%) of censored patients	xx (xx.x)	xx (xx.x)	xx (xx.x)
Reason for Censoring n(%)			
XXXXXXXXXXXXXX	xx (xx.x)	xx (xx.x)	xx (xx.x)
xxxxxxxxxxxxx	xx (xx.x)	xx (xx.x)	xx (xx.x)
Time to Progressive Disease/ Death (days)			
Quartiles (95% CI)*			
Q1	xx.x(xx.x, xx.x)	xx.x(xx.x, xx.x)	xx.x(xx.x, xx.x)
Median	xx.x(xx.x, xx.x)	xx.x(xx.x, xx.x)	xx.x(xx.x, xx.x)
Q3	xx.x (xx.x, xx.x)	xx.x (xx.x, xx.x)	xx.x (xx.x, xx.x)
Range (min, max)	(xx, xx)	(xx, xx)	(xx, xx)

The ITT analysis set includes data from all patients who received at least 1 dose of study medication.

Percentages are based on the total number of patients (N) in each treatment group.

CONFIDENTIAL

Page 44 of 106 ST-AD-032 version 01

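### SAP 5.2 reports no change although the clinical benefit rate was redefined, and stable disease of 24 weeks is set by time on drug with no single cut-off

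*SAP*

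**What the plan says.** **Protocol.** Section 8.5: "Clinical Benefit Rates: It is defined as sum of CR, PR and SD rates". Section 9.4.3: "CBR: The percentages of CR+PR+SD will be calculated and presented along with 95% confidence intervals of these percentages". Neither sets a minimum duration for SD. On revising the statistical methods, Section 9.1 says: "These methods may be revised and updated due to reasons such as regulatory requirements or need for further clarifications".

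**SAP text.** Section 6.4.2: "The percentages of CR+PR+SD>=24 weeks will be calculated and presented along with 95% confidence intervals of these percentages". Section 8.7.2: "It is defined as sum of CR, PR and SD at 24 weeks or longer". The row in Table 14.2.2.1 follows the same definition ("CBR (CR+PR+SD>=24 weeks"). Section 5.2, which exists to list departures from the protocol, says: "There were no changes in the analysis planned in the protocol of the study at the time of preparing this statistical analysis plan".

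**SAP rule for 24 weeks.** The body of the SAP does not say how 24 weeks of SD is measured. The footnote to Table 14.2.2.1 takes each patient's best overall response (BOR) and, for SD of at least 24 weeks, adds "patients with treatment duration \geq 168 (\pm 7) days are summarized". The same condition is specified for the duration of clinical benefit (DoCB) tables (14.2.4.4 to 14.2.4.6) and the duration-of-treatment plot (Figure 14.1.6.2). Treatment duration is last dose minus first dose plus 1 (SAP 8.8.1, Listing 16.2.6.6).

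**The concern.** A named secondary endpoint has two definitions, and the section meant to disclose such differences denies that there are any. Protocol 9.1 commits the study report to discussing deviations from the SAP. A change between protocol and SAP that is absent from SAP 5.2 may therefore be reported nowhere.

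The footnote is a second, separate problem. A lower limit combined with a plus-or-minus term is not one number, so two programmers could produce different counts from the same data. No scan date enters the rule, so it approximates disease status by time on drug. A patient can then be placed on the wrong side of 24 weeks, and the misplacement carries into the CBR tables, the DoCB population and the plot.

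**Working it through.** **1. The definitions side by side**

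| Source | SD component of CBR |
|---|---|
| Protocol 8.5 and 9.4.3 | any SD |
| SAP 6.4.2, 8.7.2, Table 14.2.2.1 | SD of at least 24 weeks |
| SAP 5.2 | no change declared |

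SD of at least 24 weeks is a subset of any SD, so for the same patients the SAP rate can only equal or fall below the protocol rate.

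**2. The cut-off**

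24 × 7 = 168 days, so the nominal figure reproduces. With ±7 the limit can be read as 168 − 7 = 161 days (23.0 weeks), 168 days, or 168 + 7 = 175 days (25.0 weeks). The ±7 resembles the efficacy-visit window in SAP 6.2.2, which would point to 161, but the SAP does not say so.

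**3. Scan days**

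Counting from first dose as day 1 and assuming no shift of cycles, cycle k day 1 is day 28(k − 1) + 1. C5D1 is day 113 and C7D1 is day 169; ±7 gives days 162 to 176 for C7D1, which is 15 possible days. SAP 6.2.2 gives no scheduled day for C7, so this anchoring is an assumption.

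**4. What each reading does**

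- *Cut-off 161.* Take a patient with SD at C5D1, first PD on a scan on day 162, and last dose on day 161. Duration is 161 − 1 + 1 = 161, and BOR is SD. She counts as 24-week benefit and enters the DoCB population with PD before 24 weeks. The same holds for first PD on days 162 to 167.
- *Cut-off 168.* A patient with last dose on day 165 and SD on an end-of-treatment (EOT) scan on day 170, within the 7 days allowed by protocol 6.8, has duration 165. She is not counted, although non-PD is documented past 24 weeks.
- *Cut-off 175.* The same patient is missed, as is one with SD on an on-time C7D1 scan (day 169) whose last dose is day 170.

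At 161 this miss cannot arise from an in-window EOT scan: an excluded patient's last dose is day 160 or earlier, and 160 + 7 = 167, which is before day 168.

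**5. Size of the upward error at cut-off 161**

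Assumptions not given in the documents: constant hazard; no CR or PR; no dropout; PD found only at scheduled scans; dosing continues up to the scan; C7D1 scans spread evenly over days 162 to 176. The 20% progression-free rate at 6 months is the planning value (protocol 9.2), placed at 180 days as in SAP 6.4.1.

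S(t) = 0.2^(t/180). A scan on day d falls d − 1 days after first dose. The probability that PD is first found on that scan is S(112) − S(d − 1), with S(112) = 0.3674.

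| Scan day | 162 | 163 | 164 | 165 | 166 | 167 |
|---|---|---|---|---|---|---|
| Probability | 0.1303 | 0.1324 | 0.1345 | 0.1366 | 0.1386 | 0.1407 |

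The sum is 0.813. Expected count per arm: 0.813 ÷ 15 × 20 = 1.08 of 20.

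- With 180-day rates of 10%, 30% and 40%, the same formula gives 0.92, 1.10 and 1.04.
- If only 10% or 20% of C7D1 scans fall on days 162 to 167 (mean probability 0.813 ÷ 6 = 0.1355): 0.1355 × 0.10 × 20 = 0.27 and 0.1355 × 0.20 × 20 = 0.54. Crediting all progression up to 168 days, with S(168) = 0.2227, gives (0.3674 − 0.2227) × 0.10 × 20 = 0.29, and 0.58 for 20%. The range is therefore about 0.3 to 0.6.

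**6. Effect of one patient**

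1 ÷ 20 = 5 points. For illustration, 4/20 = 20% (exact 95% CI 5.7 to 43.7%) against 5/20 = 25% (8.7 to 49.1%).

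The downward error at 168 or 175 cannot be sized, because the documents do not give the number of patients stopping drug just before the cut-off without progression.

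**The case against.** Much can be said for the plan.

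- *Revision is allowed.* Protocol 9.1 permits it, and the 24-week definition is the more demanding one. This stands: it removes any complaint about the redefinition as such. It does not make the statement in SAP 5.2 true.
- *The protocol rate is not lost.* Table 14.2.2.1 has separate ORR and SD rows with counts. If the SD row means all SD, the protocol CBR count is ORR + SD, and an exact interval follows from that count and N. This stands, on that condition. What is missing is the combined row with its interval.
- *Time on drug is related to disease status.* Confirmed progression is a reason for discontinuation (protocol 4.3), and the rule also requires BOR = SD. This stands in part: the rule is an imprecise proxy, not an irrelevant one.
- *The result can be traced.* Listing 16.2.6.6 shows response by visit, BOR and treatment duration together. True, but a listing neither corrects the reported rate nor tells the programmer which cut-off to use.

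A reader might infer that the redefinition raises CBR; a stricter definition cannot. A reader might also add the upward and downward errors of step 4 together. They arise under different cut-offs and are alternatives. Finally, SAP 5.1 says that the study closed before all patients progressed, which might suggest that closure pushed patients below the cut-off. No document shows that anyone was stopped before day 168 for that reason; the planned disposition table runs to Cycle 15 and Listing 16.2.6.6 to C19D1.

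**Conclusion.** The point holds in two parts. The first is certain on the text: CBR changed between protocol and SAP, SAP 5.2 says nothing changed, and no combined row is planned for the protocol definition. The second is that the 24-week rule has no single cut-off and uses no scan date. That ambiguity is also certain; the direction and size of any error depend on which cut-off is used.

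At 161 days the error is upward and at most about 1.1 of 20 per arm (0.9 to 1.1 for 180-day rates of 10 to 40%). That rests on the upper-end assumptions in step 5 and on counting C7D1 from first dose. It falls to about 0.3 to 0.6 if 10 to 20% of C7D1 scans come that early. At 168 or 175 days the error illustrated is downward and cannot be sized.

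A reader might go further and call it an error to count a patient whose first PD is on an on-time day-169 scan. The documents do not settle that: DoCB is timed from first dose to progression, which would put her past 24 weeks, whereas SAP 8.7.2 can be read as requiring SD to be present at week 24.

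Because CBR carries no test or decision threshold, the effect is confined to reported estimates and the DoCB population. It should be fixed, but it does not threaten the trial's primary result.

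**What to change.** 1. In SAP 5.2, list the change in CBR from CR+PR+SD to CR+PR+SD of at least 24 weeks, with the reason.
2. Add a row for CR+PR+any SD with its exact 95% CI beside the 24-week CBR, and state that the SD row means all SD.
3. Replace the treatment-duration footnote in Tables 14.2.2.1 to 14.2.2.3 and 14.2.4.4 to 14.2.4.6 and Figures 14.1.6.2 and 14.1.6.3 with one scan-date rule. SD of at least 24 weeks requires all of the following:
   - BOR = SD;
   - a documented non-PD tumour assessment at the C7D1 visit within its ±7-day window, or later, including EOT and unscheduled scans;
   - no PD or death before day 168, and none at or before that assessment.

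   State that the window is counted from first dose (days 162 to 176). The day-168 condition is needed: without it, SD on day 162 followed by PD or death on day 166 would still count.
4. Clerical only: the programmer note to Figure 14.1.6.2 names a category of SD under 4 weeks, which leaves SD of 4 to under 24 weeks without a category.

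The cost is SAP wording, one table row and one derivation from assessment data already planned for listing. The downside is that patients without a qualifying scan count as having no 24-week benefit, so CBR may come out slightly lower or higher than under the footnote.
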